## Specific Aims

Over the last decade, virtual reality (VR) has emerged as a cutting-edge technology in stroke rehabilitation. VR is defined as a type of user-computer interface that implements real-time simulation of an activity or environment allowing user interaction via multiple sensory modalities. VR interventions in a stroke population have been shown to be equivalent to usual care therapies and to enhance motor, cognitive, and psychological recovery when utilized as an adjunct. The proposed feasibility pilot project will address the RR&D goal of maximizing functional recovery by pilot testing an immersive VR intervention designed to increase exercise dosage for the upper limb and decrease pain for inpatient Veterans post stroke without increasing therapist time [1]. **The VR intervention will use a head mounted display, more commonly known as goggles, to which selected APPs can be uploaded. APPs and goggles are commercially available and have been selected based on the following criteria: (1) address the treatment goals of overall upper extremity neurologic recovery, hand dexterity, and pain reduction, (2) utilized while patient lying in bed, (3) provide no stimulation to move legs or reach outside of bed area, (4) simple to use (require no technological expertise), (5) involve graded head, neck, upper extremity movement and distraction to reduce pain, and (6) cognitive burden ranges from minimal to moderate. The VR intervention will be administered bedside for two 30-minute therapy sessions per day for four weeks. Our long-term goal is to provide Veterans with an exercise and pain reduction modality that can serve as an adjunct to scheduled therapy and assist with the clinic to home transition. Our short-term goal is to determine the feasibility of conducting a randomized controlled trial to determine the effectiveness of using VR as an adjunct to usual care therapy to enhance upper extremity neurologic recovery and hand dexterity and to decrease pain.** Our proposal is innovative in four distinct ways. First, we will use immersive 3-dimensional rather than the more typically used 2-dimensional VR. Immersion and the resulting 'presence' within the virtual environment are thought to be the principal mechanisms of positive change [2]. **Second, we will assess pain reduction after stroke using VR APPs, which is not well represented in the literature.** Third, we are using VR as an adjunct therapy - adding additional therapy time with less burden on clinicians than is required in traditional therapy. Finally, VR, when used in patients' rooms, presents an opportunity similar to home-based practice exercises. Our targeted enrollment is 10 clinical staff (Research Question (RQ) 1.1) and 10 inpatient Veterans being treated for stroke (Aim 2).

### Specific Aim 1: Determine the feasibility and tolerability of using a therapeutic VR platform in an inpatient comprehensive stroke rehabilitation program.

RQ 1.1: What is the feasibility of using the VR platform from the clinician perspective?

RQ 1.2: What is the tolerability for inpatients post-stroke using the VR platform?

### Specific Aim 2: Estimate the initial clinical efficacy, or effect size, associated with the VR platform using APPS for distraction and upper extremity exercise for Veterans post-stroke.

RQ 2.1: What are the estimated effect sizes and degree of precision for the outcomes of **upper extremity neurologic recovery, hand dexterity, and pain?**

RQ 2.2: **How clinically responsive are dexterity and upper extremity neurologic recovery (primary) outcomes to early stroke rehabilitation using a therapeutic VR platform?**

**Impact.** Veterans and clinicians will gain experience using a portable VR platform that increases access to care by making additional therapeutic activities available outside of usual scheduled therapy time. This unique experience offers the potential for seamless transition from inpatient rehabilitation to the home. Moreover, policy makers can observe firsthand the potential benefits and limitations of using therapeutic VR in comprehensive stroke care. The results of this study will inform a subsequent larger trial, which will focus on the effectiveness of immersive VR for patients in both the subacute and chronic stages post-stroke and will begin inpatient and continue post discharge into the patient's home.

Figure 1 VR intervention

## Research Plan

### Background and Significance

Over the last decade, virtual reality (VR) has emerged as a cutting-edge technology in stroke rehabilitation. VR is defined as a type of user-computer interface that implements real-time simulation of an activity or environment allowing user interaction via multiple sensory modalities [3]. VR interventions can be characterized as immersive or non-immersive. Immersion refers to the sensation of being inside a particular environment or world, for example, a three-dimensional world [4]. Non-immersive VR typically uses commercial video game systems developed by the entertainment industry for home use, although some researchers have developed rehabilitation specific non-immersive VR applications [5-7]. Non-immersive VR uses 2D interfaces such as Nintendo Wii, Microsoft Xbox, and Sony PlayStation [8-10]. Immersive VR uses a 3D virtual environment with the intention of making the user feel a part of, inside, or immersed in the environment to the extent that they become unaware of their physical surroundings [4]. Immersive VR experiences typically involve the use of a Head Mounted Display (HMD) which creates a three-dimensional image in all fields of view. We will use the most current VR technology, which at this time is a wireless immersive HMD application with hand controllers such as the Oculus Quest.

**Upper Limb VR Research.** Upper limb deficits occur in up to 85% of stroke survivors and significantly affect performance of activities of daily living (ADLs) [11]. The literature on the use of VR in stroke rehabilitation is fairly extensive, but is characterized by small, lesser quality studies with widely varying definitions of what constitutes a VR intervention. The stroke VR literature base has been criticized for lack of a control group, making it difficult to discern if positive effects were the result of the VR intervention itself or simply the result of extra therapy time, for example, when VR is used as an adjunct [12]. Studies on the use of VR for post-stroke upper limb dysfunction have shown mixed results [4-10, 13-17]. A Cochrane Review published in 2017 [18] concluded that overall effects of VR on upper extremity function were not significantly different when compared with conventional therapy (including both specialized VR systems designed for rehabilitation or commercial gaming consoles). However, when VR was utilized as an adjunct to standard care compared with no additional intervention (increased overall therapy time), the VR group experienced statistically significant benefits in upper limb function (Standardized Mean Difference (SMD) = 0.49, 95% confidence interval (CI) 0.21 to 0.77). The overall quality of the trials included for upper limb function outcomes was low. The Cochrane Review also found a small, yet statistically significant effect of VR on ADLs (SMD = 0.25, CI 0.06-0.43). Because of the heterogeneity in outcomes used in studies investigating the effect of VR on upper limb function post-stroke, two systematic reviews and meta-analyses (SR/MA) [3, 19] grouped outcomes by the International Classification of Function domains. For studies that used a virtual world environment approach to VR, medium effect sizes (ES) were found: Body Structure/Function ES = 0.43 [3] to 0.54 [19], Activity ES = 0.54 [3] to 0.62 [19], and Participation ES = 0.38 [19] to 0.56 [3]. Gains post intervention were preserved at follow up [19]. A limitation of both SR/MAs was the variability in how VR was delivered in terms of intensity and duration [3, 19] and lack of clarity regarding control group therapy.

Three recent randomized controlled trials (RCTs) [12, 20, 21] of non-immersive VR interventions (using 2D interfaces) that included control groups dose matched for therapy time found mixed results. A single-center study [21] that compared 10 sessions of a self-administered upper extremity rehabilitation program including four game applications on a smart phone and tablet with control therapy of one hour of conventional OT per day found a significant difference on the Fugl-Meyer Assessment-Upper Extremity (FMA-UE) at one-month follow-up in favor of the intervention group. In contrast, neither the EVREST trial [12] that compared 10 sessions of commercial gaming with control recreational activities or the VIRTUES multi-center trial [20] that compared 16 sessions of VR designed for rehabilitation with conventional therapy found significant differences. The authors of the EVREST study did, however, speculate that utilizing an immersive VR system might have led to significant results. As VR becomes more immersive, more interactive, and less expensive, and because of its flexibility, studies of the use of VR in the inpatient environment [22] suggest that VR is efficacious, easy to use, safe, and contributes to high patient satisfaction.

**VR and Pain.** A recent multi-site study ( $N = 546$ ) found a 30% prevalence of pain across the acute, subacute, and chronic post-stroke stages [23]. Cognitive factors (e.g., attention) are important to pain perceptions, even when people are not engaged in specific tasks [24]. Theory suggests that VR directly or indirectly affects cognitive and attentional processes to attenuate pain. VR can be a distraction

mechanism that consumes cognitive and attentional resources to limit pain processing capabilities [25]. A randomized crossover study found a 56% reduction in time thinking about pain when using VR versus self-selected distraction (e.g., meditation, smartphone;  $p < .001$ ) [26]. VR may also create neurobiological interactions in the brain by regulating sensory stimulation to produce an analgesic effect [27]. Sense of immersion and presence are important to distraction and analgesia because distraction therapy is the most commonly used intervention in VR pain research [28]. A rapid evidence assessment of VR (20 studies,  $N = 337$ ) found strong evidence for short-term reduction in pain intensity and moderate evidence for pain analgesia [29]. A meta-analysis (14 studies,  $N = 581$ ) estimated a large standardized effect (0.90, 95% CI = .72 to 1.08) for VR pain distraction studies using between-group and mixed-model designs [30]. Thus, integration of VR during rehabilitation may have promising implications for post-stroke pain.

**Neuroplasticity.** Decades of animal research and recent research in human subjects provides compelling evidence that the adult brain affected by stroke can reorganize itself in response to experience and training, with sufficient repetition playing a critical role [31-35]. In patients with subacute stroke, gains in the upper limb and hand dexterity (strength, ROM, speed of movement) require more intensive repetitive task practice than gains in lower limb and mobility [1, 36, 37]. In addition, task motivation is essential for learning [31-35]. Immersive VR exposure is hypothesized to deliver the crucial impetus to drive lasting neural changes by providing a motivating environment for post-stroke patients to retrain movement, ROM, movement speed, fractionation (use of individual fingers), and force production [38]. In the proposed study, immersive VR will be utilized as adjunct therapy, allowing patients to increase their therapy dose and thereby engage in the repetition essential for motor learning.

**Immersive VR.** Non-immersive VR environments are projected on 2D screens (e.g., laptop). Non-immersive VR can facilitate stroke symptom improvement [12, 20, 21], but it is lower on the immersion spectrum and less efficacious than immersive 3D VR [28, 39]. Immersion and presence are theoretical mechanisms of change which may facilitate greater learning within virtual environments [25, 40]. Immersive VR interventions may be cost-effective and less resource intensive than many traditional interventions with comparable efficacy [41].

**Significance.** According to the VA Informatics and Computing Infrastructure, in Fiscal Year (FY) 2018 there were more than 10,000 unique Veteran inpatient admissions for stroke. The proposed study is an innovative treatment paradigm utilizing sophisticated immersive VR technology available at the bedside to increase therapy dosage. This cutting-edge technology has the potential to not only drive neurologic recovery by augmenting the brain's own intrinsic repair capacity in response to a stroke insult (neuroplasticity), but also improve Veterans' quality of life by diminishing pain and enhancing self-efficacy. Immersive VR could ultimately become a new standard of care in acute inpatient rehabilitation, allowing unlimited rehabilitation experiences for patients with stroke. In addition, there is strong potential for seamless transition to home, as immersive VR technology rapidly becomes more sophisticated and less costly. Finally, the proposed research supports modernization of the Veterans' Health Administration by incorporating technology-assisted rehabilitation, addresses the RR&D goal of maximizing functional recovery, and focuses on VA Office of Research and Development priorities including access to care, mental health, health care value, and pain.

## Preliminary Studies

**Virtual Reality Pilot for Fear of Movement for Veterans with Chronic Pain.** In a pilot study [42, 43] in the James A. Haley Veterans' Hospital (JAHVH) inpatient Chronic Pain Rehabilitation Program, [name] and Fellow, [name], found evidence for the feasibility of VR within the chronic pain population as well as a decrease in fear of movement, pain interference with mobility, pain intensity, and pain catastrophizing. Veteran attendance (91%) and completion of attended 20-minute VR sessions was high (97%). Veterans typically rated 20-minute VR sessions as 'too short'.

## Research Design and Methods

**Design.** Our methodological framework is based on the work by Virtual Reality Clinical Outcomes Research Experts (VR-CORE) committee [39]; we will use their VR2 clinical study design: conducting early prospective testing with a focus on feasibility and tolerability (**Aim 1**), and initial efficacy (**Aim 2**). Per VR-CORE guidelines, we will use a single group so that we may optimize recruitment to represent the breadth and depth of our target patients.

**Population.** There are two populations for the proposed project. The first is Veterans ( $N=10$ ) who have been diagnosed with an acute ischemic or hemorrhagic stroke and post-stroke are admitted to JAHVH inpatient rehabilitation. Inclusion criteria are: (1) Age 18-80, (2) Stroke diagnosis verified by brain imaging. Exclusion criteria are: (1) Unable to follow instructions or participate in immersive VR therapy due to significant cognitive impairment, (2) History of seizures. The second population includes the occupational therapists (OT) and the rehabilitation nurses (clinician champions) working in the Comprehensive Interdisciplinary Inpatient Rehabilitation Program, who will provide data on the feasibility of using VR in an inpatient environment (**Research Question (RQ) 1.1**).

**Recruitment.** All patients admitted to the Comprehensive Interdisciplinary Inpatient Rehabilitation Program at JAHVH (a designated Primary Stroke Center) with a diagnosis of acute ischemic or hemorrhagic stroke will be considered for inclusion in the study. A minimum of five beds will be designated for study participants. The Comprehensive Interdisciplinary Inpatient Rehabilitation Program admits 3.5 stroke patients per month, 42 per year. We feel this is a sufficient subject pool from which to enroll the target sample size of **10** patients (**16%** of the patients admitted over the 18-month enrollment period). We have found that the technology is motivating to patients which will help retention.

**End of Data Collection.** Once all Veterans have completed the study, **RQ 1.1** feasibility data will be collected from clinician champions.

### **Outcomes**

**Aim 1.** Feasibility is the degree to which the VR treatment can be successfully integrated within the flow of usual care [15]. Feasibility will be measured with a six item survey (**Appendix 5**), based on the Consolidated Implementation Framework [44], that will be administered to 10 clinical staff using REDCap®. Tolerability refers to the prevalence of patient-reported physical (e.g., vertigo, nausea = "cybersickness") and emotional (e.g., fear and anxiety) adverse effects of the VR treatment, along with any discomfort or inconvenience related to the VR equipment (e.g., ill-fitting headset, facial discomfort, inability to explore the three-dimensional environment fully due to limited mobility, etc.) [2, 39]. Tolerability data (complaints and adverse events frequencies) will be extracted from detailed meeting minutes where such events are reported and discussed.

**Aim 2.** See **Table 2**.

**Table 2** Aim 2 Outcome variables and covariates

Variable	Definition	Source
Outcomes		
Hand dexterity Appendix 6	Action Research Arm Test (MCID*: chronic=5.7, acute=12) [45, 46] Primary	Clinical assessment and Self-report
Neurologic recovery Appendix 7	Fugl-Meyer Assessment of Motor Recovery after Stroke-UE MCID*=4-7 [47] Primary	
Pain Appendices 8 and 9	Pain Outcomes Questionnaire-VA, Initial, item 12 and Discharge, item 2 (Pain Numeric Rating Scale) (ES*= 0.85, medium effect, SEM*=0.79) [48] Secondary	
Demographic and Clinical		
Age	Age on date of baseline data collection	CPRS
Sex	Male, female	
Race/ethnicity	Caucasian, African American, Hispanic, other	
Time since index stroke	In days: index event - baseline data collection	
Type stroke	Ischemic =0, hemorrhagic =1	

\* MCID=Minimal Clinically Important Difference, ES=Effect Size, SEM=Standard Error of Measurement, CPRS=Computerized Patient Record System

**Analyses.** With the proposed pilot study design, the overall analytic goals are to: (1) determine the feasibility and tolerability of using a therapeutic VR platform in an inpatient comprehensive stroke rehabilitation program and to (2) estimate, with reasonable precision, the effect sizes of **upper extremity neurologic recovery, hand dexterity, and pain reduction outcomes**.

**Aim 1.** Qualitative descriptive analyses [49] will be used to address **RQ 1.1** (feasibility) and **RQ 1.2** (tolerability). For **RQ 1.1**, responses will be downloaded from REDCap®. The six survey items address three feasibility constructs: adaptability, patient need, and staff comments. Responses for each construct will be pasted into an excel spreadsheet, one tab for each construct. Responses will then be grouped by similar content. Results will be reported as themes and subthemes. Similarly, for **RQ 1.2**, patient concerns, complaints, and adverse events associated with use of the VR platform will be abstracted from the research team meeting notes and will be tabulated. Responses will then be grouped by similar content. Results will be reported as themes and subthemes. Note that all adverse events will be immediately reported per VA and IRB policy. The analyses described here are for dissemination purposes.

**Aim 2.** For **RQ 2.1**, the primary outcomes will consist of pre- to post-intervention changes on two physical measures of stroke recovery: the Action Research Arm Test (ARAT) [45] (Appendix 6) and the Fugl-Meyer Assessment of Motor Recovery after Stroke-Upper Extremity [47] (Appendix 7). Both of these measures are scored on a continuous scale, as is the outcome of pain, as listed in **Table 2**. Therefore, the initial step will be to examine distributions of each outcome measure, including distribution of change scores from pre- to post-intervention. To estimate effect sizes over 4 weeks with the use of the VR platform, standardized effect sizes and 95% confidence intervals will be calculated using the within-group pre-test/post-test design described by Morris and DeShon (2002) [50] and Kadel and Kip (2012) [51]. Recognizing the pilot study design, yet concern over potential type I error due to multiple outcomes evaluated, the confidence intervals for the two co-equal primary outcomes will be evaluated with a type I error rate of 0.025 (i.e. to determine if the confidence interval for the outcome difference scores includes the null effect size value of 0); secondary outcome will be evaluated with a type I error rate of 0.01. The above confidence interval approach parallels use of the paired *t*-test to determine statistical significance. For **RQ 2.1**, since the effect sizes to be calculated are standardized measures, corresponding results across these outcomes will be directly comparable. However, these metrics do not necessarily translate to meaningful clinical differences (improvements). Therefore, for those outcome measures with published metrics for minimal clinically important difference (MCID) [52], results of the VR platform will be compared across outcomes. As listed in **Table 2**, the measures of dexterity and neurologic recovery have published references for MCID, whereas we are unaware of a published MCID for the Pain Outcomes Questionnaire VA (POQ-VA). Therefore, for the POQ-VA, we will first determine the change (pre versus post scores) in

standard deviation units (from the baseline value) that denotes MCID for the measures of dexterity and neurologic recovery. We will then average these two calculations of standard deviation units to estimate the magnitude of change in pre-to-post scores on the POQ that may approximate MCID on this measure. Thus, in addition to comparison of standardized effect sizes across the three outcomes measures, all three measures will be compared in terms of proportion of subjects who experience MCID.

**Potential Limitations and Strategies.** As this pilot study will employ a within-subject design to evaluate magnitude of stroke rehabilitation over 3 weeks with the use of VR technology, there will be no control condition to judge rehabilitation results to that which might be expected from time alone and natural history of stroke recovery. Therefore, as described for **RQ 2.1**, we will place a premium on evaluating rehabilitation results using MCID, which are highly relevant to patients and generally would not be expected to be achieved simply from time alone (4 weeks).

**Project Management Plan. Personnel.** **[name]** will lead the administrative and scientific aspects of the project and will be responsible for recruitment and collection of medical data. **[name]** will oversee data management, analysis, and assist with interpretation of data. **Project Manager [name]**, an Occupational Therapist (OT), will obtain informed consent, perform pre and post data collection, **instruct study subjects in use of VR technology**, and enter data into the study dataset. **[name] and PI [name]** will perform initial technical assessment, instruct clinicians in use of VR technology, and update APPs weekly to meet individual patient needs. **[name]** will serve as a Research Mentor and can provide OT expertise. **[name]** will serve as our Program Partner from the Physical Medicine and Rehabilitation Office.

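### Does naming only 95% intervals undercut the stated error rates of 0.025 for the two primary outcomes and 0.01 for pain?

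*Combined protocol and SAP*

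**What the plan says.** The relevant text is the Aim 2 paragraph of the analysis section (under Outcomes), for RQ 2.1. One sentence, whose stated purpose is estimating effect sizes, says that "standardized effect sizes and 95% confidence intervals will be calculated using the within-group pre-test/post-test design", citing two method papers. The next sentence turns to multiplicity. It begins "Recognizing the pilot study design, yet concern over potential type I error due to multiple outcomes evaluated" and says that "the confidence intervals for the two co-equal primary outcomes will be evaluated with a type I error rate of 0.025", explained in brackets as a check "to determine if the confidence interval for the outcome difference scores includes the null effect size value of 0". For pain it says "secondary outcome will be evaluated with a type I error rate of 0.01". The paragraph then adds that "The above confidence interval approach parallels use of the paired" *t*-test.

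No 97.5%, 98% or 99% interval is named anywhere, the words one-sided and two-sided do not appear, and no overall alpha is given.

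On purpose, the analysis goals for Aim 2 are to "estimate, with reasonable precision, the effect sizes of" the three outcomes. Because there is no control group, Potential Limitations and Strategies says "we will place a premium on evaluating rehabilitation results using MCID".

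**The concern.** Read quickly, the second sentence seems to refer back to the 95% intervals just mentioned. A 95% interval checked against 0 is a two-sided test at 0.05, which is neither 0.025 nor 0.01. Read in one direction only, it gives 0.025. That fits the primaries but still not the 0.01 for pain. So no single reading of 95% delivers every stated rate, and the level that would do so is not written down.

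If an analyst did decide from the 95% intervals, the multiplicity control that the paragraph asks for would be lost. With 10 patients, a moderate observed change could then be called significant under one reading and not under the other.

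**Working it through.** **Inputs.** The 95% level and the error rates of 0.025 and 0.01 come from the Aim 2 analysis paragraph. The sample of 10 patients in one group comes from Specific Aims and from the Design paragraph. Assumptions: all 10 patients are analysed (9 df), change scores are roughly normal, and the interval is a t-interval on the mean change, in line with the paired t-test that the plan mentions.

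**Step 1: the stated rates.** 0.05/2 = 0.025, so the primary rate is an equal split of a conventional 0.05 over two outcomes. This fits the multiplicity reason given and points to a two-sided reading. The rates add to 0.025 + 0.025 = 0.05 for the primaries. If independent, the familywise rate is 1 − 0.975² = 0.0494.

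**Step 2: the implied levels.** An interval used as a test at rate α has level 1 − α when two-sided, or 1 − 2α when only one direction counts.

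| Reading | Outcome | Interval level | t (9 df) | Smallest absolute mean change/SD of change that excludes 0 (t/√10) |
|---|---|---|---|---|
| Two-sided | Primaries | 97.5% | 2.685 | 0.849 |
| Two-sided | Pain | 99% | 3.250 | 1.028 |
| One-sided | Primaries | 95% | 2.262 | 0.715 |
| One-sided | Pain | 98% | 2.821 | 0.892 |

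Once sidedness is settled, the stated rates fix the level completely.

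**Step 3: what misuse of the 95% intervals would cost.** These figures apply only if the stated rates are ignored and the reading is two-sided.

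- Familywise error for the two primaries: 1 − 0.95² = 0.0975 if independent, bounded by 0.05 + 0.05 = 0.10. Positive correlation lowers it, to about 9% at 0.5 and 7% at 0.9 by simulation.
- The verdict would differ for an observed ratio between 0.715 and 0.849 (primaries) or between 0.715 and 1.028 (pain).
- Chance of a different verdict on one primary, from the noncentral t: at a true ratio of 0.8, the 95% interval excludes 0 with probability 0.616 and the 97.5% interval with 0.475, a gap of 0.616 − 0.475 = 0.141. This is about the maximum.
- For pain at a true ratio of 0.85: 0.668 − 0.356 = 0.312, again about the maximum.

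The true ratios are assumed, since the documents give no expected change in these units.

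**Step 4: which reading the text supports.** The 95% level is attached to standardized effect sizes, in a sentence about estimation. The include-0 check is attached to the difference scores, in a sentence that carries its own error rates. The quantity, the purpose and the stated rate all change between the two sentences. Reporting 95% intervals for description while deciding at adjusted rates is coherent, and it gives both sentences their full meaning. The alternative requires the reader to discard the rates in the very sentence that defines the decision.

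**The case for a change.** The best case for a change is that the decision sentence speaks of the confidence intervals straight after 95% intervals have been named, and its bracket refers to a null value for the effect size. The natural antecedent is therefore the 95% set. Sidedness is never stated, and the mention of a paired t-test does not supply it, so the primaries could call for 97.5% or 95% and pain for 99% or 98%. The include-0 rule is spelled out only for the primaries and has to be carried over to pain. A decision fixed in advance should not depend on which reading an analyst picks after seeing the data, and a sentence or two would settle it.

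Part of this stands. The wording does blur the two uses, and the level and sidedness are indeed unwritten. But the gap is thin. The equal split of 0.05, the multiplicity reason and a rule that can be triggered in either direction all favour two-sided tests, and nothing in the text argues for one-sided ones. Carrying the include-0 rule to pain follows from the parallel clause. Writing the levels out would record what the paragraph already implies. It would not correct a wrong rate or bring in a better method.

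**Conclusion.** The concern describes the text accurately, but it does not show an error. Followed as written, the plan uses two-sided 97.5% intervals for ARAT and Fugl-Meyer and a 99% interval for pain when deciding, with the 95% effect-size intervals as description. That gives at most 0.05 across the two primaries and 0.01 for pain, as intended. The familywise figure of up to 10%, and the chances of a different verdict of about 14% (one primary) and 31% (pain), describe misuse of the plan under assumed true effects, normal change scores and complete data. They are not consequences of following it.

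Little rests on these decisions in any case. The aim is estimation in 10 patients, no design choice or progression rule uses the rates, and the plan gives most weight to minimal clinically important differences. Without a control group, excluding 0 at any interval level cannot separate an effect of virtual reality from natural recovery. The conclusion rests on the two-sided reading. If the rates were meant one-sided, the levels would be 95% and 98%, and they would still follow from the stated rates. No change to the plan follows.

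### With no baseline pain requirement, the all-patient pain effect size is capped by how many of the 10 patients rate pain above 0, and the two-sided 0.01 test cannot reject with fewer than 6

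*Combined protocol and SAP*

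**What the plan says.** Pain is the only secondary outcome, a single numeric rating taken before and after the intervention (Table 2). Under Analyses, Aim 2 (RQ 2.1), all three outcomes get a standardized within-group pre/post effect size with an interval. The interval is then used "to determine if the confidence interval for the outcome difference scores includes the null effect size value of 0", and for pain the level is set by "secondary outcome will be evaluated with a type I error rate of 0.01". The plan adds: "The above confidence interval approach parallels use of the paired *t*-test to determine statistical significance". It also says of the standardized effects that "corresponding results across these outcomes will be directly comparable".

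Enrolment does not depend on pain. Under Research Design and Methods, Population: "Inclusion criteria are: (1) Age 18-80, (2) Stroke diagnosis verified by brain imaging". And: "Exclusion criteria are: (1) Unable to follow instructions or participate in immersive VR therapy due to significant cognitive impairment, (2) History of seizures". The target is 10 Veterans. No section restricts the pain analysis to patients who have pain or says what to do with baseline ratings of 0. Use of all 10 is therefore the default reading, although no sentence states it.

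The only pain prevalence in the documents is in Background and Significance, where a multi-site study "found a 30% prevalence of pain across the acute, subacute, and chronic post-stroke stages".

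**The concern.** A patient who rates pain 0 before treatment can only stay at 0 or get worse. Each such patient pulls the mean reduction towards zero and, when others improve, widens the spread of the change scores. With 10 patients, the size of the pain effect and the outcome of its test may be settled largely by how many enrolled patients have pain to lose.

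Two statements in the plan then cause trouble. The 0.01 rule may be unable to reject whatever VR does. The comparability statement invites a reader to rank pain against dexterity and neurologic recovery, when the pain figure carries a ceiling set by case mix. Pain reduction is one of the stated innovations and the results are meant to inform a larger trial, so a capped, non-significant effect could be carried forward as if it measured weak pain relief.

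**Working it through.** **The plan's own figures.** There is no power, precision or sample-size calculation for pain or for N = 10, so there is no design figure to reproduce. The one piece of arithmetic attached to N, in Recruitment, is correct: 10/(3.5 × 18) = 15.9%, stated as 16%.

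**Inputs.** n = 10 (Specific Aims; Population). Level 0.01 and paired t analogy (Analyses, Aim 2). Sidedness is not stated, so both are shown. With 9 degrees of freedom the critical t is 3.25 two-sided and 2.82 one-sided. Prevalence 30% (Background). Two assumptions are needed to use it: that it applies to this unit, and that it means a rating above 0.

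**The bound.** Let x be each patient's pain reduction, S the sum and Q the sum of squares over the 10 patients. Then t² = 9S²/(10Q − S²). If only k patients can have a positive x, Cauchy-Schwarz gives S² ≤ kQ whenever S is positive. Worsening in a patient who started at 0 lowers S and raises Q, so it cannot help. Hence

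- maximum t = 3√(k/(10−k))
- maximum mean change/SD of change = maximum t/√10

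The maximum is reached when all k patients improve by the same amount. The same cap holds for mean change divided by the baseline SD, because the mean reduction cannot exceed the baseline mean.

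| k rating above 0 | Maximum t | Two-sided p at that t | Maximum effect size |
|---|---|---|---|
| 2 | 1.50 | 0.168 | 0.47 |
| 3 | 1.96 | 0.081 | 0.62 |
| 4 | 2.45 | 0.037 | 0.77 |
| 5 | 3.00 | 0.015 | 0.95 |
| 6 | 3.67 | 0.005 | 1.16 |

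Rejection at two-sided 0.01 needs k ≥ 6. At one-sided 0.01 it needs k ≥ 5. Listing every combination of ratings 1 to 10 for k = 3 gives the same maximum, 1.96.

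**Worked case.** At 30%, the expected k is 0.30 × 10 = 3. Suppose three patients fall from 5 to 0 and seven stay at 0. The mean reduction is 15/10 = 1.5, SD 2.415, SE 2.415/√10 = 0.764, and t = 1.5/0.764 = 1.96. The 99% interval is 1.5 ± 3.25 × 0.764, or −0.98 to 3.98. Even the 95% interval (critical t 2.26) is −0.23 to 3.23. Complete relief in every patient with pain gives an interval that includes 0.

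**Chance that rejection is possible at all.** Taking k as Binomial(10, prevalence):

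| Share rating above 0 | k ≥ 6 (two-sided) | k ≥ 5 (one-sided) |
|---|---|---|
| 20% | 0.6% | 3.3% |
| 30% | 4.7% | 15.0% |
| 40% | 16.6% | 36.7% |
| 50% | 37.7% | 62.3% |

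These are upper limits: they assume that pain is abolished and that reductions are equal. If baseline ratings in those with pain were uniform on 3 to 8 (an assumption), 4.7% becomes about 3.9%.

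**Case mix.** Complete relief from one common baseline rating gives an effect size of 0.47 if 2 patients have pain and 1.16 if 6 do. The treatment effect in those patients is identical; only enrolment differs.

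**The case against.** A reader might infer that the pain test is bound to fail in this trial even if VR abolished all pain. The documents do not support that, for three reasons.

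- The 30% is a background figure pooled over stroke stages. It is not a planning assumption for this inpatient unit.
- The background passage does not define pain, so the share rating above 0 may be higher. If the other seven patients each fell from 1 to 0 while three fell from 5 to 0, t would be 3.60 and the test would reject.
- Even at 30%, k varies from sample to sample. The impossibility is exact only for a given k.

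A reader might also set the cap against the 0.85 in Table 2 or the 0.90 meta-analytic effect in Background. Neither is a stated target for this trial. The first is listed with the measurement properties of the pain measure, and the second comes from between-group and mixed-model studies.

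It is fair to add that pain is secondary, that the aim is estimation, and that no go/no-go rule depends on the test. The plan also examines distributions first, which would reveal the zeros, and it warns that standardized effects need not be clinically meaningful. That lowers the stakes, but no action is attached to the look at distributions, and the 0.01 rule and the comparability statement remain as written.

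Finally, an all-patient mean is a legitimate estimate if the later trial keeps the same eligibility. Restricting to patients above 0 invites regression to the mean in a study without controls. It may also leave almost nobody: at 30%, P(k ≤ 1) = 0.7¹⁰ + 10 × 0.3 × 0.7⁹ = 0.028 + 0.121 = 15%. Both points stand, so the subset should accompany the all-patient estimate and not replace it.

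**Conclusion.** The concern holds in conditional form. If all 10 patients are analysed, as the plan implies by default, the number rating above 0 at baseline caps the standardized pain reduction, and fewer than 6 such patients (fewer than 5 if one-sided) makes rejection at 0.01 arithmetically impossible. That bound needs no prevalence figure.

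How likely this is depends on the two assumptions about the 30%. Under them, rejection is possible in at most 4.7% of samples two-sided or 15% one-sided; at 50% the two-sided figure is still only 38%. A non-significant or moderate pain result could not be read as evidence of weak pain relief, and the pain effect size is not on an equal footing with the motor ones. For a 10-patient pilot this is a wording problem in the analysis, worth correcting because the correction is cheap.

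**What to change.** In Analyses, Aim 2 (RQ 2.1):

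1. Drop the 0.01 significance rule for pain.
2. Report how many patients have a baseline pain rating of 0.
3. Give the all-patient pain change with its interval. Beside it, give the change in patients with a baseline rating above 0, with an interval if there are enough of them and with each pre/post pair listed.
4. State that the subset estimate is open to regression to the mean, since there is no control group.
5. Exclude pain from the statement that standardized effects can be compared directly across outcomes.

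The cost is analysis wording only: no extra patients, visits or measurements. The downside is that the pilot makes no significance claim for pain, and the subset estimate may rest on very few patients.
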